7.5.2 Progression Free Survival

PFS is defined as the time from the date of first dosing until the date of objective disease progression as defined by Lugano classification or death (by any cause in the absence of progression) regardless of whether the patient discontinues the study treatments.

Patients who have not progressed or died at the time of analysis will be censored at the time of the latest date of assessment from their last evaluable tumor response assessment.

Note: Symptomatic deterioration will not be regarded as a progression event.

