4.1.2.3 PFS assessed by IRC based on CT

PFS is defined as the time from the date of first dosing until the date of objective disease progression as defined by Lugano classification or death (by any cause) regardless of whether the participant discontinues the study treatments. Progression is identified based on CT imaging evaluated by IRC. Participants who have not progressed or died at the time of analysis will be censored at the time of the latest date of assessment from their last evaluable tumor response assessment. More censoring rules for PFS are presented in Table 1. Symptomatic deterioration will not be regarded as a progression event.

The PFS will be calculated as:

$$\text{PFS (months)} = (\text{date of event/censoring} - \text{first dose date of AZD4205} + 1) / 30.4375.$$

Table 1 Censoring Scheme for PFS

No.	Situation	Date of Progression or Censoring	Outcome
1	No baseline or any post-baseline tumor assessments and without death within two visits (112 days from date of first dose)	Date of first dose	Censored

Statistical Analysis Plan of PTCL (Version 3.0)

Protocol Code: DZ2019J0005 (Part B)

Date: Mar 25, 2023

No.	Situation	Date of Progression or Censoring	Outcome
2	No baseline or any post-baseline tumor assessments and died within two visits (112 days from date of first dose)	Date of death	Event
3	Progression documented between scheduled visits	Date of first radiological PD	Event
4	No progression at the time of data cut-off/discontinuation from the study	Date of last visit with *adequate radiological tumor assessment prior to data cut-off or discontinuation from the study.	Censored
5	Treatment discontinuation for reason other than radiological PD	Data after discontinuation of treatment will be included when determining the time to progression	Event / Censored
6	New anticancer treatment started	Date of last adequate radiological tumor assessment with documented non-progression before start of new treatment	Censored
7	Death before first PD assessment	Date of death	Event
8	Death between scheduled tumor assessment visits	Date of death	Event
9	Death or progression after more than one missed visit (CT scans will be done for tumor assessments within 7 days of Day 1 of Cycle 3, 6, 9 and then every 3 cycles thereafter until PD)	Date of last adequate radiological tumor assessment with documented non-progression	Censored

* Adequate tumor assessment is a radiologic assessment of CR, PR, SD, non-CR/non-PD or PD as determined by investigators.

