5.5.3 Sensitivity Analysis

No sensitivity analysis will be conducted.

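### SAP Table 1 censors some known deaths that the PFS definition counts as events, other rows of the same table count them, and no precedence or sensitivity analysis is given

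*SAP*

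**What the plan says.** Protocol 7.5.2 makes PFS end at progression or at "death (by any cause in the absence of progression) regardless of whether the patient discontinues the study treatments". Its censoring rule is equally plain: "Patients who have not progressed or died at the time of analysis will be censored at the time of the latest date of assessment" of the last evaluable scan. SAP 4.1.2.3 repeats this: "Participants who have not progressed or died at the time of analysis will be censored at the time of the latest date of assessment". It then refers to Table 1 for further censoring rules.

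Four rows of Table 1 matter here:

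- Row 1, "No baseline or any post-baseline tumor assessments and without death within two visits (112 days from date of first dose"): censored at first dose.
- Row 7, "Death before first PD assessment": event at the date of death.
- Row 8, death between scheduled assessment visits: event at the date of death.
- Row 9, "Death or progression after more than one missed visit": censored at the last adequate assessment showing no progression.

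SAP 4.1.2.1 ties the end of response, and the censoring time for DoR, to the PFS dates. SAP 5.5.3 reads in full: "No sensitivity analysis will be conducted".

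**The concern.** There are two faults. First, rows 1 and 9 censor patients who are known to have died, although the definition in the protocol and in the same SAP section counts those deaths. Second, rows 7 and 8 carry no limit on elapsed time or missed scans, so they claim the same deaths as events. The table does not say which row wins, and two programmers following it literally could build different PFS datasets.

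Patients who stop attending scans before they die may not be typical of those still scanned, so the censoring may be informative. Part B is meant to support a marketing application, and PFS and DoR will be read next to the response rate. With sensitivity analysis excluded, the report would contain no estimate under the protocol's own rule.

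**Working it through.** **1. The plan's own figure.** Rows 1 and 2 use a two-visit limit of 112 days. Cycles last 21 days and scans fall on Day 1 of Cycles 3, 6, 9 and every third cycle after, each ±7 days. The second scan, C6D1, is 5 × 21 = 105 days after first dose, and 105 + 7 = 112. The figure reproduces. With first dose as study day 1, the scans fall on days 43, 106, 169 and 232.

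**2. Applying the rows literally.** PFS in months = (end date − first dose date + 1) / 30.4375 (SAP 4.1.2.3).

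Patient A has no post-baseline scan and dies on day 150, after missing C3D1 and C6D1. Patient B has stable disease at C3D1 (day 43), misses C6 and C9, and dies on day 200.

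| Rule | Patient A | Patient B |
|---|---|---|
| Protocol 7.5.2 and SAP text | event, 150/30.4375 = 4.93 | event, 200/30.4375 = 6.57 |
| Row 1 | censored, 1/30.4375 = 0.03 | does not apply |
| Row 7 | event, 4.93 | depends on the meaning of first PD assessment |
| Row 8 | event, 4.93 (day 150 lies between days 106 and 169) | event, 6.57 (day 200 lies between days 169 and 232) |
| Row 9 | censored, but no qualifying scan supplies a date | censored, 43/30.4375 = 1.41 |

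Rows 1 and 9 agree with each other on censoring. The opposition is rows 7 and 8 against rows 1 and 9.

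**3. DoR.** Patient A cannot enter DoR, because SAP 4.1.1 classes a patient without a post-baseline assessment as a non-responder. Now give Patient B a partial response at C3D1 instead. Under row 8, DoR is an event at (200 − 43 + 1)/30.4375 = 158/30.4375 = 5.19 months. Under row 9 it is censored at (43 − 43 + 1)/30.4375 = 0.03 month.

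**4. Size.** The documents give no rate of missed scans, so size can only be illustrated. Two simulations used the trial's scan schedule; their other inputs are assumptions.

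- *Scan dropout unrelated to progression.* Median time to progression was 3.5 or 5 months and to death 8 or 12 months; 10%, 20% or 30% of patients stopped scanning after 0 to 2 scans; cut-off was 24 months, with 6,000 patients per scenario. Giving rows 1 and 9 precedence moved about 4 to 12 deaths per 100 patients from event to censored. Events per 100 were 93 to 99 with all deaths counted and 81 to 95 under rows 1 and 9. The 6-month PFS rate was about 2 to 8 percentage points *lower* under rows 1 and 9 (for example 0.253 against 0.176). The median was unchanged in nine of the twelve scenarios, where it sat at the second scan (105/30.4375 = 3.45 months). The largest shift was 4.578 − 3.475 = 1.10 months, shorter under rows 1 and 9.
- *Deaths as first event after two missed scans in 5% to 21% of patients* (100 patients, 400 runs, exponential PFS). The medians differed by about 0.1 month or less at an underlying median of 3.5 months and by 0.2 to 0.3 month at 5 months. At longer medians PFS was *longer* under the SAP rules: 8.16 − 7.87 = 0.29 month with 7% censored, and 8.68 − 7.73 = 0.95 month with 21% censored. If the lost patients had already progressed, the difference was at most 0.15 month.

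The two simulations move in opposite directions. DoR was not simulated.

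**The case against.** Censoring after missed scans is a legitimate analysis choice. A late death may stand in for an earlier progression that nobody saw, and counting it at the date of death then overstates PFS. The SAP introduces Table 1 as adding to the text, and the rows can be reconciled by letting the specific beat the general. If row 7 governed no-scan deaths, row 1's day limit would do nothing for them; if row 8 governed every death, the mention of death in row 9 would be redundant. Reading row 7 as meaning before the first scheduled scan would also remove its conflict with row 1. Finally, SAP 5.5.2.2 requires a breakdown of events and censorings and SAP 5.7.1 lists all deaths, so the censoring will be visible.

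Much of this is fair, and it limits the point. But the reconciling reading is not written. Narrowing row 7 alone leaves row 8 against row 9. Resolving everything towards censoring leaves the departure from the stated definition. A count of censored patients does not re-estimate PFS. Since neither rule is free of assumptions, the sound course is to state one and show the other.

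A reader might also charge row 6 (new anticancer treatment) with the same fault. Row 6 does leave later deaths uncounted, but Protocol 6.9.1 says images after new therapy are not collected, and row 6 parallels how the primary estimand in SAP 2.1.1 treats new therapy. It needs to be stated clearly in any sensitivity analysis; it is not part of the contradiction.

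**Conclusion.** The point holds. As written, Table 1 gives some patients two outcomes, and rows 1 and 9 censor deaths that the protocol and the SAP's own text count. The SAP cites protocol version 5.0 and the protocol supplied is version 6.0, but this does not explain the conflict, because it sits inside SAP 4.1.2.3.

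Three stronger inferences are not supported:

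- *That the rule inflates PFS.* The direction depends on why patients stop scanning, which the documents do not tell us.
- *That the bias is large.* Protocol 2.1 cites PFS of 3 to 4 months on existing treatment, and near that level the simulated effect on the median was mostly about 0.1 month or less. Shifts of roughly 1 month needed longer medians and heavy scan dropout, both assumed.
- *That the main result is at risk.* PFS and DoR are secondary Kaplan-Meier summaries without a test. The ORR test and its 84.5% power do not depend on Table 1.

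The case for change rests on the contradiction and the missing check.

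**What to change.** 1. Make the rows of Table 1 mutually exclusive. Limit rows 7 and 8 to deaths not covered by rows 1, 2, 6 or 9, and limit row 9 to patients with at least one adequate post-baseline assessment. Patient A then meets row 1 only and Patient B row 9 only. A written order of precedence would serve equally well. Editing row 7 alone would not, because rows 8 and 9 would still clash.
2. State in SAP 4.1.2.3 that censoring after missed visits is a deliberate departure from Protocol 7.5.2.
3. Replace SAP 5.5.3 with one pre-specified sensitivity analysis of IRC-assessed PFS and DoR, counting deaths and IRC-documented progressions at their actual dates regardless of missed visits. Say how new anticancer therapy is handled: later images are not collected, so progressions after it cannot be counted, and the analysis shows sensitivity to the rule without being an unbiased reference.

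The cost is table wording and two extra Kaplan-Meier runs. Death dates already come from the survival follow-up in Protocol 3.1.3, so no new data are needed.

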During the study treatment, CT scans of the same sites with screening should be performed for tumor response assessments within 7 days of Day 1 of Cycle 3, 6, 9 and then every three cycles

until confirmed disease progression, death or withdraw from the study. For patients with confirmed bone marrow involvement at baseline, if complete remission is suspected based on radiological imaging, the bone marrow aspiration/biopsy should be done at the same visit to confirm the involvement status. Clinical response of progressive disease (PD), stable disease (SD), partial response (PR), or complete response (CR) should be determined at each assessment according to 2014 Lugano classification (see Table 9).

Any patient who discontinues study treatment for reasons other than disease progression should have response assessment performed as scheduled in the protocol until disease progression or death occurs, unless consent is withdrawn.

Table 14 CT-based response categories per 2014 Lugano classification

Response	Site	CT-based response criteria
_	Target lesion(s)	All of the following: - Target nodes/nodal masses must regress to ≤ 1.5 cm in LDi - No extra-lymphatic sites of disease
Complete	Non-measured lesion(s)	Absent
response	Organ enlargement	Regress to normal
	New lesion(s)	None
	Bone marrow	Normal by morphology; if indeterminate, IHC negative
Partial response	Target lesion(s)	 All of the following: ≥ 50% decrease in SPD of up to 6 target lesions When a lesion is too small to measure on CT, assign 5 mm ×5 mm as the default value When no longer visible, 0 mm × 0 mm For a node > 5 mm × 5 mm, but smaller than the normal, use actual measurement for calculation
	Non-measured lesion(s)	Absent/normal, regressed, but no increase
	Organ enlargement	Spleen must have regressed by > 50% in length beyond normal
	New lesion(s)	None
	Bone marrow	Not applicable
	Target lesion(s)	< 50% decrease from baseline in SPD of up to 6 target lesions; no criteria for progressive disease are met
Stable	Non-measured lesion(s)	No increase consistent with progression
disease	Organ enlargement	No increase consistent with progression
	New lesion(s)	None
	Bone marrow	Not applicable

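### SAP Table 1 sets censoring dates for IRC-assessed PFS and DoR by investigator reads instead of IRC reads

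*SAP*

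**What the plan says.** SAP 4.1.2.3 is headed as IRC-assessed PFS on CT, and its text fixes the reader for the event: "Progression is identified based on CT imaging evaluated by IRC". The general censoring sentence, which begins "Participants who have not progressed or died at the time of analysis will be censored", points to the last evaluable assessment without naming a reader. Protocol 7.5.2 does not name one either.

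Table 1 then adds detailed rules. Row 4 (no progression at cut-off or study discontinuation), row 6 (new anticancer treatment) and row 9 ("Death or progression after more than one missed visit") all date censoring at the last *adequate* radiological assessment. The only definition of that word is the footnote: "Adequate tumor assessment is a radiologic assessment of CR, PR, SD, non-CR/non-PD or PD as determined by investigators". The asterisk that leads to it is printed in row 4 only.

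SAP 4.1.2.1 defines IRC-assessed DoR from IRC response and progression, and a responder who has not progressed takes the PFS censoring time. SAP 4.1 names the IRC data source as participant-level results, including best response, progression date and first-response date. SAP 4.1.2.5 makes investigator-assessed PFS and DoR a separate set of secondary endpoints.

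**The concern.** A time-to-event endpoint should take its events and its censoring dates from the same reader. Here the IRC decides whether and when a patient progressed, while the site decides how long the patient is counted as known to be progression-free. If the IRC could not evaluate the last scan, the IRC has no evidence of freedom from progression on that date, yet the patient stays at risk until then. If only the IRC could evaluate the scan, follow-up that the IRC did observe is thrown away.

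Part B is a single-arm study meant to support a marketing application, and IRC-assessed DoR and PFS are its durability evidence. Neither of the planned comparisons repairs the date. The concordance analysis in Protocol 7.5.1 compares IRC and investigator results, and SAP 4.1.2.5 repeats the endpoints by investigator.

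**Working it through.** **Inputs**

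- Scans within 7 days of Day 1 of Cycles 3, 6 and 9, then every 3 cycles; 21-day cycles (SAP 4.1.1 and 2.2).
- PFS in months = (event or censoring date − first dose date + 1)/30.4375 (SAP 4.1.2.3).
- DoR in months = (event or censoring date − first response date + 1)/30.4375 (SAP 4.1.2.1).

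**The plan's own figure.** The scan day is (cycle − 1) × 21 + 1: C3 = day 43, C6 = day 106, C9 = day 169. Table 1 gives 112 days for two visits. C6 Day 1 is 5 × 21 = 105 days after first dose, and 105 + 7 = 112. The figure reproduces, so this is the calendar on which Table 1 works.

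**Which reader sets each date**

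| Quantity | Reader under the SAP text |
|---|---|
| Progression date, IRC PFS | IRC |
| First response date, IRC DoR | IRC |
| Censoring date, row 4 | Investigator (footnote, asterisk printed) |
| Censoring date, rows 6 and 9 | Investigator, if the same word carries the same meaning (no asterisk) |
| Censoring date, IRC DoR | As for PFS |

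Row 4 does not ask for documented non-progression, and the footnote counts PD as adequate. Read literally, the censoring scan could be one that the site called PD and the IRC could not evaluate.

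**Size per patient**

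- *Too late, usual case.* Interval = 106 − 43 = 63 days; 63/30.4375 = 2.07 months. Take a patient with a first IRC response on day 43, a day-106 scan read as PR by the site but not evaluable to the IRC, and no later scan. PFS is censored at 106/30.4375 = 3.48 months under the footnote and at 43/30.4375 = 1.41 on IRC reads. DoR is censored at (106 − 43 + 1)/30.4375 = 2.10 and (43 − 43 + 1)/30.4375 = 0.03.
- *Too late, Cycle 3 scan.* If the only post-baseline scan is on day 43 and the IRC cannot evaluate it, censoring on IRC reads would fall back to first dose: 43/30.4375 = 1.41 against 1/30.4375 = 0.03 months, a gap of 42 days.
- *Too early.* If the day-106 scan is evaluable to the IRC but not to the site, with no later scan, the footnote censors at 1.41 months where the IRC reads support 3.48.

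**Size for the whole sample.** The documents give no rate of reader disagreement, so every input here is assumed. The simulations cover only scans evaluable to the site and not to the IRC, occurring at random.

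PFS: 90 patients, exponential times, 25% of failures are deaths, follow-up 240–600 days, scan dates ±7 days, 400 runs per setting.

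| True median (months) | Not evaluable to IRC | Median PFS, site v IRC censoring (months) | Censored patients dated late |
|---|---|---|---|
| 4 | 5% | 5.04 v 5.04 | 0.78 of 11.7 |
| 4 | 10% | 5.13 v 5.13 | 1.63 of 11.7 |
| 5 | 5% | 5.93 v 5.92 | 1.08 of 17.3 |
| 5 | 10% | 6.05 v 6.03 | 2.31 of 17.2 |

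Six-month PFS changes by 0.1 point or less.

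DoR: 27 responders (27% of 100), true median 6 or 9 months, 15% deaths, follow-up 183–550 days after response, 1,500 runs. At 10% not evaluable, the 6-month rate is 60.8% v 60.6% and 71.9% v 71.7%, a difference of 0.2 point.

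**The case against.** The strongest defence is that the footnote was written for the investigator endpoints, where it is correct, and that the independent review charter supplies the IRC date. The charter is cited in SAP 1 but was not available for this review, and the list of IRC sources in SAP 4.1 is introduced as *including* its items, so it need not be complete. This limits what can be said: the absence of an IRC last-evaluable date cannot be established. It does not rescue the footnote, which stands under an IRC heading, names the investigator and has no IRC counterpart in the SAP or protocol.

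Four stronger readings are tempting, but the documents do not support them.

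- *The rows of Table 1 contradict each other.* Row 1 ("No baseline or any post-baseline tumor assessments and without death within two visits (112 days from date of first dose") censors at first dose, while row 7 ("Death before first PD assessment") counts an event; row 8 ("Death between scheduled tumor assessment visits") and row 9 overlap in the same way. But if row 7 covered every patient who died unscanned, row 2 and the 112-day limit would have no purpose. If row 8 covered every death between visits, the mention of death in row 9 would do little. Reading rows 1, 2 and 9 as exceptions to rows 7 and 8 gives each row an effect. SAP 4.1.2.3 also introduces Table 1 as further censoring rules, so its general sentence is not contradicted. An explicit order is missing detail, not an error.
- *Non-CR/non-PD is a stray category to delete.* Protocol Appendix VI does not list it: "Clinical response of progressive disease (PD), stable disease (SD), partial response (PR), or complete response (CR) should be determined at each assessment". Nor does SAP 5.5.1. But PFS uses the evaluable for survival set (SAP 3.6), which does not require measurable disease, so the category may be needed for patients with only non-measured lesions.
- *The error always lengthens follow-up.* It runs in both directions, as shown above.
- *The decision in SAP 5.5.3 to run no sensitivity analysis is part of this fault.* It is a separate choice and does not follow from the footnote.

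**Conclusion.** The point stands as a minor error. The written rule takes censoring dates for IRC-assessed PFS from site reads, and IRC-assessed DoR inherits them. Row 4 is certain. Rows 6 and 9 follow on the natural reading of a shared word. For an affected patient the date is usually wrong by 63 days, or by 42 days at Cycle 3 if censoring falls back to first dose, and it can be too late or too early.

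The effect on the estimates is negligible: about 0.02 months or less in median PFS and 0.2 point or less in the 6-month DoR rate. This rests on an assumed 5–10% of scans evaluable to the site only, unevaluable at random. The reverse disagreement was not simulated, and unevaluability linked to disease course could act differently. The primary ORR test, its sample size of 100 and its stated power of 84.5% do not depend on Table 1.

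**What to change.** 1. Reword the Table 1 footnote so that an adequate assessment is determined by the IRC for IRC-assessed endpoints and by investigators for investigator-assessed endpoints. Mark it on rows 4, 6 and 9.
2. In SAP 4.1, name the IRC time-point responses, or the IRC's last evaluable date, as the source of the censoring date.
3. Keep non-CR/non-PD, or map it explicitly to SD.

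Optional clarification: state that rows 1, 2 and 9 are exceptions to rows 7 and 8, and that row 6 applies only when new therapy starts before IRC progression. Row 6 must not override an earlier progression. For example, with a scan on day 43, unscheduled IRC progression on day 80 and new therapy on day 90, row 3 gives an event at 80/30.4375 = 2.63 months, whereas row 6 would censor at 1.41.

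A separate suggestion is one supportive run of IRC PFS and DoR that counts every documented IRC progression and every death. Images after new therapy are not collected (Protocol 6.9.1), so after a switch this would mainly add deaths.

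Cost: one footnote change and one named data source. The optional items add a sentence or two and one more run of existing code, whose estimates may be less favourable than the main ones.

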4.1.2.4 TTR assessed by IRC based on CT

TTR will be derived from those participants who had a CR or PR only.

TTR assessed by IRC based on CT is defined as the time from the date of first dosing to the time of the initial response of PR or CR. Response is identified based on CT imaging evaluated by IRC.

The algorithm for TTR is provided below:

TTR (months) = (date of first response – first dose date of AZD4205 + 1)/30.4375.

Statistical Analysis Plan of PTCL (Version 3.0)

Protocol Code: DZ2019J0005 (Part B)

Date: Mar 25, 2023

